6.6. High-dose Safety Assessment

After 9 evaluable patients in the Safety Lead-in have completed one 28-day cycle of treatment, safety assessments will be conducted. All toxicities will be assessed for severity by the Investigator using CTCAE v4.03. Evaluable patients for the Safety Lead-in cohort must have either:

- experienced a DLT (Table 7) or
- received at least 75% of the planned cumulative dose of both study drugs during Cycle 1.

The Sponsor and participating Investigators will perform ongoing reviews of patient safety data through regular teleconferences approximately weekly during the Safety Lead-in. Once 9 evaluable patients are available for assessment, the Sponsor will convene a joint teleconference with participating Investigators. If the high-dose treatment is found safe based on 9 evaluable patients, subsequent patients will be randomized 1:1 to receive either the standard or high-dose treatment. If the high-dose treatment is determined not to be safe, enrollment will proceed with the standard-dose treatment as outlined in Section 4.1. The high-dose treatment will be considered safe if the rate of DLTs (Table 7) observed in the first cycle of treatment in the Safety Lead-in is $< 33\%$.

Table 7. Criteria for Defining Dose-limiting Toxicities

DLT Definition
A DLT is defined as any AE or laboratory abnormality that is not explained by underlying disease, disease progression, intercurrent illness, or concomitant therapies that either meets the criteria described below or results in the inability to tolerate at least 75% of the planned dose of binimetinib or encorafenib during Cycle 1.
Specific DLT Criteria
Cardiac disorders 
 • Absolute decrease of LVEF > 10% compared to baseline and the LVEF is below the institution's LLN • LV systolic dysfunction Grade ≥ 3 • Other cardiac disorders Grade ≥ 3
Vascular disorders 
 • Grade 3 hypertension for > 14 consecutive days • Grade 4 hypertension
Skin and subcutaneous tissue disorders^a 
 • Rash, hand foot skin reaction (HFSR) or photosensitivity CTCAE Grade 3 for > 14 consecutive days despite maximal skin toxicity treatment (as per local practice) • Rash, HFSR or photosensitivity CTCAE Grade 4
Gastrointestinal disorders^a 
 • Diarrhea Grade 3 for ≥ 48 hours despite optimal use of antidiarrheal therapy • Diarrhea Grade 4 • Nausea/vomiting Grade 3 for > 48 hours despite optimal use of antiemetic therapy
Investigations 
 • Total bilirubin Grade ≥ 3 • AST or ALT Grade ≥ 3 in conjunction with total bilirubin Grade ≥ 2 of any duration • AST or ALT Grade 3 for > 7 consecutive days • AST or ALT Grade 4 • Serum creatinine Grade ≥ 3 • CK elevation ≥ Grade 3 associated with an increase in creatinine ≥ 1.5 × the patient's baseline screening creatinine • ANC Grade 4 for > 7 consecutive days • Platelet count Grade 3 with signs of clinically significant bleeding • Platelet count Grade 4 • ECG QTcF prolonged ≥ Grade 3^b
Eye disorders – Retinal 
 • Retinopathy or retinal detachment Grade ≥ 3, confirmed by ophthalmic examination • Retinal vascular disorder including RVO, confirmed by ophthalmic examination
Eye disorders – Visual disturbances without ocular (retinal) changes 
 • Blurred vision, flashing lights, floaters: Grade ≥ 3
Eye disorders – Other (specify) 
 • Grade ≥ 3 for > 21 consecutive days • Grade 4 confirmed by ophthalmic examination
Other hematologic and nonhematologic toxicities^c 
 • Any other Grade ≥ 3 AE except: 
 a. Lymphocyte count decreased (lymphopenia) Grade ≥ 3 unless clinically significant
Renal dysfunction 
 • Calculated GFR decrease of 50% from baseline • Proteinuria 24-hour urine protein > 2 g/24 hours

a. Prophylactic treatment for nausea/vomiting or skin AEs is not required with binimetinib. However, antiemetics and treatments for skin AEs should be used at the discretion of the Investigator if the patient experiences nausea/vomiting and/or skin AEs Grade ≥ 1.

b. QTcF must be prolonged on 2 separate ECGs.

c. Isolated laboratory changes (e.g., alkaline phosphatase, cholesterol, lipase, serum amylase) or those due to sampling or laboratory errors without associated clinical signs or symptoms may be determined to not be reviewable toxicities upon review and agreement by the Investigator and Sponsor Medical Monitor.

6.6.1. Management and Follow up of Reviewable Toxicities

Patients who experience a reviewable toxicity will receive appropriate treatment and supportive care as necessary and will be monitored closely until resolution of the toxicity to baseline or the event appears to have stabilized for a minimum of 2 weeks (14 days). During follow up, patients should be seen as often as medically indicated to assure safety.

6.6.2. Procedure for High-dose Safety Review

The Sponsor and Investigators will perform a safety review of the high-dose treatment arm after there are 9 evaluable patients in the Safety Lead-in. An evaluable patient is defined in [Section 6.6](#). The Sponsor and participating Investigators will also perform an ongoing weekly review of safety data to assess tolerability and safety during the Safety Lead-in. A Steering Committee will be consulted throughout the study on topics including ongoing individual toxicities and AEs ([Section 9.6.1](#)).

Routine safety monitoring is described from [Section 7.3](#) through [Section 7.6](#).

6.7. Dose Modification

6.7.1. General Procedures for Dose Modification

Treatment with encorafenib and binimetinib may be delayed, allowing for resolution of toxicity. Patients may resume treatment if no medical condition or other circumstance exists that, in the opinion of the Investigator, would make the patient unsuitable for further participation in the study. Patients should resume study treatment within 2 weeks of the scheduled interruption, unless otherwise discussed with the Sponsor. The Investigator should contact the Sponsor Medical Monitor to discuss the case of any patient whose treatment has been delayed for more than 2 weeks (14 days) before restarting study treatment.

Instructions for dose modifications and interruptions are outlined in [Appendix 2](#) (encorafenib) and [Appendix 3](#) (binimetinib). Individual decisions regarding dose interruptions and modifications should be made using appropriate clinical judgment in consultation with the Sponsor Medical Monitor, considering relatedness of the AE to the study treatment and the patient's underlying condition. Adverse events that have a clear alternative explanation, or transient (≤ 72 hours) abnormal laboratory values without associated clinically significant signs or symptoms may be exempt from dose-reduction rules as clinically appropriate. Dose interruptions are permitted in the case of medical or surgical events or logistical reasons not related to study treatment (e.g., elective surgery, unrelated medical events, patient vacation, holidays). The reason for interruption will be documented in the patient's study record. All dose modifications are based on the worst preceding toxicity.

Doses of encorafenib and binimetinib may be independently delayed and reduced for toxicity management as outlined in [Table 8](#). The Investigator should refer to and follow the labeled guidance (if applicable) and/or institutional guidelines for the management of toxicities relating to encorafenib and binimetinib. Detailed guidelines can also be found in [Appendix 2](#) and [Appendix 3](#).

When the AE that resulted in a dose reduction improves to and remains stable to the patient's baseline for a minimum of 14 days, the dose can be re-escalated up to the starting dose level (450 mg encorafenib QD plus 45 mg binimetinib BID) at the discretion of the Investigator, provided there are no other concomitant toxicities that would prevent drug re-escalation. There is no limit to the number of times the patient can have their dose reduced or re-escalated; however:

- No dose re-escalation of encorafenib is allowed after a dose reduction due to prolonged QTcF \geq 501 msec;
- No dose re-escalation of binimetinib is allowed after a dose reduction due to LVEF dysfunction;
- No dose re-escalation of binimetinib or encorafenib is allowed after a dose reduction due to ocular toxicity \geq Grade 2.
- Patients who are receiving 600 mg encorafenib QD plus 45 mg binimetinib BID who require a dose reduction are not permitted to re-escalate (see [Section 6.7.2](#)).

Table 8. Dose Reductions for Encorafenib and Binimetinib

Level	Dose
Dose Reduction for Encorafenib in the High-dose Combination Arm	
0 (starting dose)	300 mg BID
-1	225 mg BID
-2	150 mg BID
-3	75 mg BID ^a
Dose Reduction for Encorafenib in the Standard-dose Combination Arm	
0 (starting dose)	450 mg QD
-1	300 mg QD
-2	225 mg QD ^b
Dose Reduction for Single-agent Encorafenib^c	
-1	300 mg QD
-2	225 mg QD ^b
Dose Reduction for Binimetinib (both arms)	
0	45 mg BID
-1	30 mg BID ^d

Table 8. Dose Reductions for Encorafenib and Binimetinib

Level	Dose
-------	------

NOTE: Dose reduction is based on the highest AE grade.

- a. Dose reduction below 75 mg BID is not allowed.
- b. Dose reduction below 225 QD is not allowed.
- c. Single-agent encorafenib dose reduction applies to patients who have permanently discontinued binimetinib.
- d. Dose reduction below 30 mg BID is not allowed.

If a patient misses > 28 consecutive days of dosing with combination treatment (both encorafenib and binimetinib), study treatment will be discontinued unless, in the opinion of the Investigator, the patient will derive clinical benefit from continued treatment. The Investigator will discuss this decision with the Sponsor Medical Monitor. If a patient permanently discontinues binimetinib (i.e., no dose for > 28 days), the patient may continue single-agent encorafenib if, in the opinion of the Investigator, the patient is deriving clinical benefit. Doses of single-agent encorafenib are decreased to a maximum of 300 mg QD when binimetinib is permanently discontinued.

If a patient permanently discontinues treatment with encorafenib, he or she must discontinue treatment with binimetinib.

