2.2.4. Clinical Safety of Encorafenib as a Single Agent in the COLUMBUS Study

The maximum well-tolerated dose of encorafenib when given as a single agent is 300 mg daily. Encorafenib 300 mg daily as a single agent is associated with an increased risk of certain AEs compared to when used in combination with binimetinib. For example, Grade 3 or 4 dermatologic reactions in the COLUMBUS study occurred in 21% of patients treated with single-agent encorafenib compared to 2% of patients treated with encorafenib in combination with binimetinib. Among patients receiving single-agent encorafenib 300 mg QD across multiple clinical trials including COLUMBUS, the most common AEs ($\geq 20\%$, all grades) were alopecia (50%), palmar-plantar erythrodysesthesia syndrome (48%), arthralgia (43%), hyperkeratosis (42%), nausea (35%), dry skin (29%), fatigue (28%), myalgia (28%), headache (27%), vomiting (25%), rash (23%) and palmoplantar keratoderma (22%).

Detailed information regarding clinical safety of encorafenib is presented in the encorafenib Investigator's Brochure.

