Appendix 3. Recommended Dose Modifications for Binimetinib-related* Adverse Events

Severity of Adverse Event	Dose Modifications
Cardiomyopathy	
Asymptomatic, absolute decrease in LVEF of > 10% from baseline that is also below the LLN	Withhold binimetinib for up to 4 weeks, evaluate LVEF every 2 weeks. Resume binimetinib at a reduced dose if the following are present: 
 • LVEF is at or above the LLN and • Absolute decrease from baseline is 10% or less and • Patient is asymptomatic. If LVEF does not recover within 4 weeks permanently discontinue binimetinib.
Grade 3-4 (Symptomatic congestive heart failure or absolute decrease in LVEF of > 20% from baseline that is also below LLN)	Permanently discontinue binimetinib. Closely monitor LVEF until resolution or up to 16 weeks.
Venous Thromboembolism	
Uncomplicated DVT or PE	Withhold binimetinib. 
 • If improves to Grade 0-1, resume at a reduced dose. • If no improvement, permanently discontinue binimetinib.
Life threatening PE	Permanently discontinue binimetinib.
Serous Retinopathy	
Symptomatic serous retinopathy/ Retinal pigment epithelial detachments	Withhold binimetinib for up to 10 days. 
 • If improves and becomes asymptomatic, resume at the same dose. • If not improved, resume at a lower dose level or permanently discontinue binimetinib.
Retinal Vein Occlusion (RVO)	
Any Grade	Permanently discontinue binimetinib.
Uveitis	
Grade 1-3	If Grade 1 or 2 does not respond to specific ocular therapy, or for Grade 3 uveitis, withhold binimetinib and encorafenib for up to 6 weeks. 
 • If improved, resume at same or reduced dose. • If not improved, permanently discontinue binimetinib.
Grade 4	Permanently discontinue.
Other Eye Disorders (i.e., Non-retinal Events, non-Uveitis Events)	
Grade 1-2	Maintain dose level of encorafenib and binimetinib and increase frequency of ophthalmic monitoring to at least every 14 days until stabilization or resolution.
Grade 3	Interrupt dosing of encorafenib and binimetinib and refer patient to ophthalmologist within 7 days.

Severity of Adverse Event	Dose Modifications

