	
 If resolved to Grade ≤ 1 in ≤ 21 days, resume treatment at 1 reduced dose level of encorafenib and binimetinib. If not resolved to Grade ≤ 1 in ≤ 21 days, permanently discontinue encorafenib and binimetinib and close follow-up with ophthalmic monitoring until stabilization or resolution.
Grade 4	Permanently discontinue encorafenib and binimetinib and immediate follow-up with ophthalmic monitoring until stabilization or resolution.
Interstitial Lung Disease	
Grade 2	Withhold binimetinib for up to 4 weeks. 
 If improved to Grade 0-1, resume at a reduced dose. If not resolved within 4 weeks, permanently discontinue.
Grade 3 or Grade 4	Permanently discontinue.
Hepatotoxicity	
Grade 2 AST or ALT increased	Maintain binimetinib dose. 
 If no improvement within 2 weeks, withhold binimetinib until improved to Grade 0-1 or to pretreatment/baseline levels and then resume at the same dose.
Grade 3 or 4 AST or ALT increased	See Other Adverse Reactions
Rhabdomyolysis or Creatine Phosphokinase (CPK) elevations	
Grade 4 asymptomatic CPK elevation or Any Grade CPK elevation with symptoms or with renal impairment	Withhold binimetinib dose for up to 4 weeks. 
 If improved to Grade 0-1 resume at a reduced dose. If not resolved within 4 weeks, permanently discontinue binimetinib.
Dermatologic	
Grade 2	If no improvement within 2 weeks, withhold until Grade 0-1. Resume at same dose if first occurrence or reduce dose if recurrent.
Grade 3	Withhold until Grade 0-1. Resume at same dose if first occurrence or reduce dose if recurrent.
Grade 4	Permanently discontinue.
Nausea/Vomiting	
Grade 1-2	Maintain dose level of encorafenib and binimetinib. Promptly institute antiemetic measure.
Grade 3	Interrupt dosing of encorafenib and binimetinib until resolved to Grade ≤ 1 . Then resume treatment at 1 reduced dose level of encorafenib. Resume treatment with binimetinib at the current dose if, in the judgment of the Investigator, the toxicity is considered to be unrelated to binimetinib, or at 1 reduced dose level.

Severity of Adverse Event	Dose Modifications
	Note: Interrupt dosing of encorafenib and binimetinib for \geq Grade 3 vomiting or Grade 3 nausea only if the vomiting or nausea cannot be controlled with optimal antiemetics (as per local practice).
Grade 4	Permanently discontinue encorafenib and binimetinib.

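### The 300 mg limit on encorafenib without binimetinib begins only at permanent discontinuation, so a temporary binimetinib-only hold can leave a patient on 450 or 600 mg QD alone

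*Protocol*

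**What the plan says.** Section 2.2.4 of the protocol states: "The maximum well-tolerated dose of encorafenib when given as a single agent is 300 mg daily". It adds that Grade 3 or 4 dermatologic reactions "occurred in 21% of patients treated with single-agent encorafenib compared to 2% of patients treated with encorafenib in combination with binimetinib".

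The operative rule is in Section 6.7.1: "Doses of single-agent encorafenib are decreased to a maximum of 300 mg QD when binimetinib is permanently discontinued". The same paragraph explains the term: "If a patient permanently discontinues binimetinib (i.e., no dose for > 28 days". Note c to Table 8 has the same scope: "Single-agent encorafenib dose reduction applies to patients who have permanently discontinued binimetinib".

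Section 6.7.1 also lets the two drugs be delayed independently. Six Appendix 3 rows use this and withhold binimetinib only:

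- asymptomatic LVEF fall: "Withhold binimetinib for up to 4 weeks, evaluate LVEF every 2 weeks"
- symptomatic serous retinopathy: "Withhold binimetinib for up to 10 days"
- CPK elevation: "Withhold binimetinib dose for up to 4 weeks"
- Grade 2 interstitial lung disease: up to 4 weeks
- uncomplicated DVT or PE: no time limit
- Grade 2 AST or ALT without improvement by 2 weeks: until recovery

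None of these rows gives an encorafenib dose for the hold. Meanwhile Section 6.7.2 says that Phase 2 patients who tolerate Cycle 1 and meet the criteria should go from 450 to 600 mg QD.

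**The concern.** The reason for a single-agent limit is that encorafenib is less well tolerated without binimetinib. That applies from the first day binimetinib is withheld, yet the limit waits until the stop is permanent. Whether permanent is read as more than 28 days without a dose or as a decision to stop, a temporary hold falls outside it.

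A site also has reason to read silence as no change. The footnote to Appendices 2 and 3 says guidance for the other drug is given where an event may relate to both, and the uveitis, Grade 3 other-eye and Grade 3 nausea/vomiting rows do name both. A binimetinib-only row therefore suggests leaving encorafenib alone.

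The current rules also penalise caution. An investigator who lowers encorafenib from 600 mg during a hold risks this being counted as a dose reduction, after which Sections 6.7.1 and 6.7.2 bar a return to 600 mg. If the event is ocular toxicity of Grade 2 or higher, Section 6.7.1 bars any re-escalation. At stake are exposure above the protocol's own single-agent limit and different practice from site to site.

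**Working it through.** The plan gives no figure to reproduce, so this is a comparison of texts plus dose arithmetic.

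**1. Grade 2 AST or ALT, the one row where the text is explicit.** Appendix 2 keeps the encorafenib dose and withholds it only if there is no improvement by 4 weeks. Appendix 3 withholds binimetinib if there is no improvement by 2 weeks. With both clocks started at onset, the gap is 4 − 2 = 2 weeks, or 14 days of encorafenib alone at the current dose.

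**2. The other five rows.** They neither maintain nor lower encorafenib. Sections 6.7.2 (intolerance of 600 mg) and 6.7.3 (renal triggers) do not cover a binimetinib hold, and no other text sets a dose.

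**3. Ratio to the limit.** 450/300 = 1.5; 600/300 = 2.0.

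**4. Encorafenib taken without binimetinib, daily dose × days (mg).**

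| Hold | At 300 | At 450 | At 600 |
|---|---|---|---|
| 10 days (serous retinopathy row) | 3,000 | 4,500 | 6,000 |
| 14 days (AST/ALT gap; also the 2-week resume rule in 6.7.1) | 4,200 | 6,300 | 8,400 |
| 28 days (4-week rows; past 2 weeks only after Sponsor discussion) | 8,400 | 12,600 | 16,800 |

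Beyond 28 days the stop counts as permanent and the existing cap applies, so the open-ended DVT/PE row has the same ceiling.

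**5. How often (Section 2.2.3).** LVEF decrease 7%, symptomatic serous retinopathy 8%, venous thromboembolism 6%, pneumonitis 0.3%. These are upper bounds for the hold rows: the LVEF figure includes symptomatic falls, the thromboembolism figure is not limited to uncomplicated cases, the pneumonitis figure is not limited to Grade 2, and patients already at 300 mg or less are unaffected. The shares meeting the CPK and Grade 2 AST/ALT rows are not given.

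**6. Dose given up under a cap.** At 450 mg: 150 × 14 = 2,100 mg to 150 × 28 = 4,200 mg. At 600 mg: 300 × 14 = 4,200 mg to 300 × 28 = 8,400 mg. As a share of total encorafenib, with constant dosing and one hold:

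- assumed 24 weeks (168 days; totals 75,600 and 100,800 mg): 2.8 to 5.6% at 450 mg, 4.2 to 8.3% at 600 mg
- assumed 12 weeks (84 days; totals 37,800 and 50,400 mg): 5.6 to 11.1% at 450 mg, 8.3 to 16.7% at 600 mg

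**The case against.** The strongest reply is that the rule is deliberate. Section 6.7.1 and Table 8 note c agree with each other, Section 2.2.4 is background rather than a dosing instruction, and the AST/ALT rows suggest that full-dose encorafenib during a short hold was contemplated. It is true that no two operative rules conflict. But no rationale is given for exceeding the stated single-agent limit, and five of the six rows are silent.

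A second reply is that Section 6.7.1 already requires clinical judgment in consultation with the Medical Monitor, a return to treatment within 2 weeks unless discussed with the Sponsor, and use of labeled guidance if applicable. These are real controls, but as written in the protocol they set no dose. The label is not among the documents, so whether it fills the gap at 450 mg cannot be judged here. Section 2.2.1 describes the approved encorafenib dose as 450 mg QD, so reliance on the label is weaker still at 600 mg.

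A third reply stands in full. A reader might take the 21% versus 2% figures as the harm from full-dose encorafenib during a hold. They are not: the single-agent COLUMBUS dose was 300 mg QD, which is the cap itself, and the comparison is not for short holds. The figures show poorer tolerability without binimetinib, not the effect of going above 300 mg.

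Finally, a cap takes encorafenib away, for binimetinib-related events, from patients with active brain metastases, and a loosely worded cap would collide with the ocular re-escalation bar and the Cycle 1 escalation criteria. Both points stand and shape the wording of the fix.

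**Conclusion.** The gap is real. Followed as written, the protocol allows encorafenib alone at 1.5 to 2 times its own single-agent maximum for up to 28 days, and for Grade 2 AST or ALT it directs this for about 14 days.

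Two stronger readings should be avoided. One is that the protocol requires 450 or 600 mg throughout every binimetinib hold; only the AST/ALT rows say to maintain the dose. The other is that exposure above the limit is unbounded; the more-than-28-day definition ends it.

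The added risk cannot be quantified, because the documents give no single-agent data at 450 or 600 mg and none for short holds. The number of patients affected is probably modest. The conclusion rests on treating Section 2.2.4 as the protocol's own view of single-agent tolerability. On that basis the text should be changed, because the correction is cheap and the protocol already uses a temporary encorafenib cut with return to the previous dose for moderate CYP3A4 inhibitors (Section 6.5.1.1).

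**What to change.** In Section 6.7.1 and Table 8 note c, add: *While binimetinib is withheld for toxicity, encorafenib is given at no more than 300 mg QD; the previous encorafenib dose may be resumed when binimetinib is resumed.*

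State that this temporary cap does not count as a dose reduction for:

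- the bar on returning to 600 mg
- the re-escalation bar after ocular toxicity of Grade 2 or higher
- the 14-day stability condition for re-escalation in Section 6.7.1
- the Section 6.7.2 criterion of no reductions in Cycle 1, so that a hold within the permitted single interruption of up to 4 days does not block escalation

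Cross-reference the sentence in the six Appendix 3 rows and align the Grade 2 AST/ALT row of Appendix 2. In SAP Sections 6.5.3 and 6.5.3.1, report capped patients and capped days separately. Leave the relative dose intensity denominator unchanged, or show the result both ways, so that capped days are not reported as full intensity. If the sponsor does intend full-dose encorafenib during short holds, the protocol should state that dose and the reason.

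The cost is a short protocol amendment and a clarifying line in the SAP, with no new assessments and no change in sample size. The clinical price is the temporary, reversible loss of 150 or 300 mg of encorafenib per day during the hold, in patients with active brain metastases.
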